4.0 Subject Considerations

4.1 Subject Selection and Enrollment Considerations

A. Method to Identify Potential Subjects

At each site, patients will be identified through electronic medical record review of active patients and by referrals from treating physicians/nurses/social workers. Research study staff will contact treating physicians or other qualified treatment team member familiar with the patients, to assess

medical eligibility of patients. If a physician or other treatment team member feels their patient is not suitable for participation, we will not approach the patient. Patients who pass initial screens will be approached in person by research staff during a routine medical visit or contacted by letter/phone or email (if available).

B. Recruitment Details

Trained research staff will approach potentially eligible patients during a routine medical visit or via letter/phone, or e-mail (if available). If in-person, study staff will hand out the study information sheet and flyer, explain the study, assess interest/eligibility, allow adequate time for review and discussion with family if needed, and obtain informed consent if patient is eligible and interested. If by letter/phone, study staff will mail study cover letter along with the study information sheet and flyer to explain the study and let them know they will be contacted by phone by a member of the study team to assess interest and eligibility. If patient's email address is available, an email will be sent to introduce the study and to let them know the study staff will follow-up with a phone call. Staff will be rigorously trained as to how to approach patients, introduce the study, communicate about confidentiality and voluntary participation, and engage in the process of informed consent in a culturally-competent way.³⁹ Recruitment scripts, cover letter, information sheet, e-mail wording and flyer are being uploaded for approval.

C. Subject Screening

A study staff member will screen interested patients during their initial contact. Study staff member will approach potentially eligible patients (i.e., within the age range and with initial physician/nurse/social worker's recommendation) in clinic, send a recruitment letter/email, or call, if not scheduled for a visit, using the Recruitment Script to explain the study and answer any questions from potential participants. If the patient is interested, study staff member will administer the Eligibility Checklist. If patient is eligible and willing to enroll in the study, the study staff member will continue the Consent process.

Inclusion Criteria

Participants will be eligible if:

- 1) Current age 18-39 years
- 2) Within 4 months of first* diagnosis of any cancer (*patients diagnosed previously with non-melanoma type of skin cancer treated with surgery only may also be included).
- 3) Cancer is being treated with chemotherapy and/or radiation therapy and/or hematopoietic stem cell transplant (immunotherapy included)
- 4) No documented or self-reported cognitive delay or impairment that would prevent completion of survey measures
- 5) English-speaking

Exclusion Criteria

- 1) Life expectancy < 6 months per physician/treatment team report
- 2) Treatment involves surgery only

4.2 Secondary Subjects

N/A

4.3 Number of Subjects

A. Total Number of Subjects

344

B. Total Number of Subjects If Multicenter Study

C. Feasibility

Each site has a large enough patient population to support recruitment of the target number of participants. Combined across sites, the estimated patient pool is 3,450 over 3 years; acceptance rates would have to fall below 10% to not meet accrual goals, which is highly unlikely given our acceptance rate of 66% in our pilot study.

4.4 Consent Procedures

A. Consent Process

Location of Consent Process

The consent process will take place during a patient's routine medical visit (in-person or telehealth), or via phone.

Ongoing Consent

The trainers conducting the intervention sessions will also be trained to check in with participants at each session their ongoing willingness to participate in the study. Each follow-up survey will begin with a paragraph of instructions reminding participants of the voluntary nature of their participation.

Individual Roles for Researchers Involved in Consent

The PI, project coordinator, or trained research staff member will obtain consent.

Consent Discussion Duration

We expect most initial consent discussions to take approximately 10 minutes. The trainers conducting the intervention sessions will also be trained to check in with participants at each session about their ongoing willingness to participate in the study.

Coercion or Undue Influence

The PI or trained research team member obtaining consent is not a part of the treating team and will clearly state that participation is voluntary and the decision to take part in the study or not will have no effect on the person's ongoing treatment or relationship with their treating team.

Subject Understanding

The PI or trained research team member obtaining consent will encourage questions and ask the participant to state in their own words their understanding of the research study, including risks, benefits, and voluntary nature of participation. The consent form will contain a few questions to assess understanding.

B. Waiver or Alteration of Consent Process

Waiver or Alteration Details

N/A

Destruction of Identifiers

N/A

Use of Deception/Concealment

N/A

a. Minimal Risk Justification

N/A

b. Alternatives

N/A

c. Subject Debriefing

N/A

C. Documentation of Consent

Documenting Consent

Informed consent will be obtained from every participant prior to beginning the study via online DatStat consenting (with electronic signature). In the event of internet disruption or technical difficulties, paper consent can be used. Signed consent forms can be securely downloaded from DatStat and stored in Rutgers BOX or as indicated in site-specific local context procedures.

 Waiver of Documentation Of Consent (i.e., will not obtain subject's signature) N/A

4.5 Special Consent/Populations

A. Minors-Subjects Who Are Not Yet Adults

Parental Permission

N/A

Non-Parental Permission

N/A

Assent Process

N/A

Documentation of Assent

NI/A

Reaching Age of Majority During Study

N/A

B. Wards of the State

N/A

Research Outside of NJ Involving Minors

C. Non-English-Speaking Subjects

N/A

Process for Non-English-Speaking Subjects

N/A

Short Form Consent for Non-English Speakers

N/A

D. Adults Unable to Consent / Decisionally Impaired Adults

N/A

NJ Law-Assessment of Regaining the Capacity to Consent

N/A

Capacity to Consent

N/A

a. NJ Law-Selecting A Witness

Ν/Δ

b. Removing a Subject

N/A

4.6 Economic Burden and/or Compensation for Subjects

A. Expenses

There are no costs associated with this study.

B. Compensation/Incentives

Participants will receive a \$25 gift card for each of the first four completed surveys, and a \$50 gift card for completing the final survey, up to \$150 total. Small token gifts, such as Bright IDEAS stress balls or sticky pads, will be sent as a thank you for participants' time and effort to promote retention in the study. Furthermore, to promote retention, study staff will mail yearly holiday cards to subjects on study.

C. Compensation Documentation

Research staff will maintain documentation of compensation in DatStat, which keeps records of the compensation sent electronically to participants.

4.7 Risks of Harm/Potential for Benefits to Subjects

A. Description of Risks of Harm to Subjects

Reasonably Foreseeable Risks of Harm

This study involves minimal risk. There are no physical risks or side effects associated with the study. Potential emotional risks of study participation include possible discomfort or distress associated with answering survey questions about current emotional functioning, problem-solving skills, financial strain, and health-related quality of life, or discussing personal challenges during problem-solving sessions. Attending in-person sessions may be seen as an inconvenience, but virtual visits are available and the trainer attempts to minimize burden by scheduling when the participant is already scheduled for a medical visit or offering virtual sessions as needed. There is also a risk of breach of confidentiality of data provided for research, but safeguards are in place to minimize risks (see section E. Minimizing Risks below). Based on our prior experience conducting research with cancer caregivers, the likelihood that participants in this study will experience such discomfort or distress is low.

Risk of Harm from an Intervention on a Subject with an Existing Condition All participants will be undergoing cancer treatment and the intervention is targeted to address the needs of these individuals. Individuals with a concurrent or past mental health diagnosis are eligible to participate and trainers or the PI can make referrals for additional psychological treatment resources as needed if participants present with mental health concerns.

Other Foreseeable Risks of Harm

A possible loss of confidentiality could cause embarrassment for a participant but unlikely to cause any social harm or consequences given no collection of sensitive data.

 Observation and Sensitive Information N/A

B. Procedures which Risk Harm to Embryo, Fetus, and/or Pregnant Subjects

C. Risks of Harm to Non-Subjects

N/A

D. Assessment of Social Behavior Considerations

Participant distress will be systematically monitored in several ways. First, the study coordinator at each site will review patient reported distress on the baseline survey. Individuals who report elevated distress scores (i.e., ≥8 on 0-10 scale) will be assessed for safety, and if they express no intent to harm themselves, will be referred to clinical social work services. If there is concern about participant safety in the medical setting, the study will alert the treating clinical staff to initiate patient safety protocols and notify the site PI (licensed psychologist). If the participant is not at the medical center, research staff will coach them to go to their nearest emergency room for help and call 911 if needed. Second, interventionists will be trained to respond to patient distress at the time it occurs during intervention sessions, calling the Site PI (licensed psychologist) and referring to clinical social work services if needed. Third, study coordinators will review patient-reported distress at all subsequent surveys, intervening as above if elevated distress occurs and documenting procedures.

E. Minimizing Risks of Harm

Participants will be encouraged to contact the research team if they experience emotional discomfort or distress at any time during the study. All research staff will receive training to appropriately identify and handle instances when a patient would benefit from a referral (e.g., to a clinical social worker) for follow-up of emotional discomfort or distress.

To protect the confidentiality of participants, a series of security procedures will be undertaken. IRB and HIPAA regulations concerning confidentiality will be strictly enforced. All study personnel receive training and certification in human subjects protection and HIPAA regulations. Each study participant will be given a unique numeric identifier upon study entry. Names and other identifiable protected health information will not be stored in the same database as survey and

medical information. All computers used for research purposes adhere to the institution's requirements regarding password protection, data encryption, anti-virus protection, and intrusion detection. All Internet-based data communications will be encrypted. This includes transfer of electronic audio files between approved members of the research team for treatment fidelity and supervision purposes if needed. All hard copy study-related materials and data will be stored in locked file cabinets in the site Pl's locked office.

Certificate of Confidentiality

This study is NIH-funded and therefore a Certificate of Confidentiality is automatically issued to protect the data collected.

Provisions to Protect the Privacy Interests of Subjects

Participants will only be approached by trained and authorized research staff. Physicians or other appropriate treatment team members will be contacted for permission to approach prospective participants that study staff deem eligible based on the inclusion criteria. If anyone feels their patient is not suitable for participation, we will not approach the participant.

F. Potential Benefits to Subjects

Participants randomized to the Bright IDEAS-YA intervention may benefit by improving problem-solving skills and reducing symptoms of anxiety, depression, and distress. Prior studies with caregivers of pediatric patients have demonstrated such benefits²⁰⁻²² but it is unknown if AYA would benefit from this training. Participants randomized to the Enhanced Usual Care arm may or may not benefit from obtaining the list of resources from the NCCN adolescent and young adult patient guideline.

5.0 Special Considerations

5.1 Health Insurance Portability and Accountability Act (HIPAA)

HIPAA language is included in the consent form. As part of this study the following identifiable and/or protected health information will be collected: name, address, phone number, date of birth, email address, date of diagnosis, and IP address (surveys completed on DatStat collect this data but IP address will not be downloaded with the survey data). We will not be disclosing individually identifiable health information unless required by law.

5.2 Family Educational Rights and Privacy Act (FERPA)

N/A

5.3 Code of Federal Regulations Title 45 Part 46 (Vulnerable Populations)

A. Special Populations

Prisoners: N/ANeonates: N/A

Neonates of Uncertain Viability: N/A

Children: N/A

Individuals with Impaired Decision-Making Capacity: N/A

5.4 General Data Protection Regulation (GDPR)

N/A

5.5 NJ Access to Medical Research Act (Surrogate Consent)

N/A

6.0 Data Management Plan

6.1 Data Analysis

Aim 1: Efficacy of the Bright IDEAS-YA intervention vs. enhanced usual psychosocial care will be evaluated assuming repeated measures linear models, using maximum likelihood estimation (MLE) (SAS Proc Mixed).⁴⁰ All randomized participants, regardless of the extent to which they completed the intervention, will be included in intent-to-treat analysis. The benefits of this approach include: (1) all available data can be included in analyses; (2) correlation between related measures and adjusted test statistics can be estimated; (3) time varying covariates (such as school/employment status, treatment status (on treatment vs. completed), utilization of usual psychosocial care) can be incorporated into the model; and, (4) the assumptions about missing data from Missing Completely at Random (MCAR) to Missing at Random (MAR) are relaxed. Site will be included as a fixed effect. The primary hypothesis is that participants in Bright IDEAS-YA will experience greater decreases in depression and anxiety and increases in HRQOL at the 6month follow-up relative to participants in the enhanced usual psychosocial care condition. The primary endpoint will be the estimated change from baseline to 6 months in depression, anxiety, and psychosocial HRQOL (i.e., Social/Family Well-Being and Emotional Well-Being), calculated as linear contrasts of regression parameters using the main effect of time and the interaction between time and treatment group from the mixed linear model. The changes from baseline to 3 months, 12 months, and 24 months will be considered secondary endpoints. For HRQOL, we are particularly interested in 12-and 24-month followups given that changes may take longer to accrue compared with distress symptoms. Sensitivity analyses will be performed to determine the robustness of conclusions.⁴¹ Planned sensitivity analyses include: (1) analysis with and without adjusting for site; (2) per protocol analysis (excluding participants who did not complete at least 4 out of 6 intervention sessions, selected because it is expected that participants would have adequate exposure and practice with the Bright IDEAS model by four sessions); (3) adjustment for imbalance in baseline characteristics, if applicable; and (4) analysis to examine any differences by racial/ethnic subgroups.

Aim 2: Mediation analysis will be used to evaluate problem-solving ability as a mediating variable between the intervention and each of the outcomes while also allowing for a direct effect of intervention on outcome. Specifically, bootstrap approaches will estimate the proportions attributed to the direct effect and to the effect mediated through problem-solving using the R program package mediation.⁴²

A small direct effect is expected due to a positive therapeutic effect of talking to the trainer. Problem-solving ability will be measured by the total scale score and five subscales (positive problem orientation, negative problem orientation, rational problem solving, impulsive-careless style, and avoidant style), which will each be considered individually as potential mediators.

Aim 3: Potential moderators, including sex, financial strain, baseline unmet needs, and baseline distress, will be tested individually in models including all possible interaction terms. We will allow for each moderator to interact with time, arm, and time x arm to determine if it modifies the relationship between intervention and outcomes. We consider this analysis exploratory to identify subgroups who may benefit differentially from this intervention. We expect that females and participants with greater financial strain, baseline unmet needs, and baseline distress will benefit more.

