1.3 Research Design and Methods

Bright IDEAS-YA will be tested with young adult cancer patients in a two-arm parallel randomized controlled trial (RCT) of the intervention versus enhanced usual psychosocial care.

A. Research Procedures

Research staff will collect participants' contact information for tracking and study management. Following consent, baseline surveys (see section 1.9 Data Collection) will be administered online using DatStat, a HIPAA-compliant electronic data capture system. Research staff will either provide a tablet for patients to complete the online survey (paper copies will be available as back-up in the event of significant internet disruption) or email/text a link for completion. If a participant does not complete the baseline survey during an initial in-person visit, we will email a link for completion. After completion of the baseline survey, participants will be randomly assigned 1:1 to either the intervention or enhanced usual psychosocial care comparison group. The study biostatistician will determine a randomization scheme stratified by site, age group (18-29 vs. 30-39 based on definitions of emerging adults and young adults¹⁸)using an undisclosed block size to balance group assignment within each site and age group. This schema will be uploaded to the DatStat program such that completion of the baseline survey will trigger assignment according to the schema via a message to study staff. Participants will then be notified of assignment via an automatic Welcome email through DatStat. For those assigned to the intervention group, study staff will assign a Bright IDEAS-YA trainer, schedule for the participant and trainer to meet at the patient's next medical visit or schedule a virtual meeting to complete the first Bright IDEAS-YA session, and mail/email Bright IDEAS-YA manual, worksheets and the list of resources from the NCCN adolescent and young adult patient guildeline. 19 For those assigned to the enhanced usual psychosocial care group, study staff will mail/email the list of resources from the NCCN adolescent and young adult patient quidelines. 19 All participants will also be mailed a small gift (e.g., Bright IDEAS stress ball) as a token of appreciation for their time and effort. Trainers will schedule all subsequent sessions directly with participants. All participants will be asked to complete surveys at 3 months (post-intervention), 6 months (3-month follow-up), 12 months (9-month follow-up), and 24 months (21-month followup). DatStat will send survey links and subsequent reminders via email/text according to the survey schedule. Study staff will also call and/or send text message reminders to participants to facilitate completion of online surveys as needed. All participants will continue to receive usual psychosocial care per institutional standards, as well as a standardized list of young adult-specific resources (see Enhanced Usual Psychosocial Care section). Usage of these services will be tracked via patient self-report at each survey. Participants will receive \$25 for each of the first four surveys completed, and a \$50 gift card for completing the final survey (up to \$150 total).

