- o Financial strain, a marker of socioeconomic status particularly relevant for young adults with cancer, will be measured using the Comprehensive Score for Financial Toxicity (COST),³⁴ an 11-item scale of financial toxicity associated with cancer treatment. Respondents rate each item on a 5-point Likert scale from 0 (*not at all*) to 4 (*very much*) in the past 7 days. The measure yields a total summary score, with higher scores indicating greater financial strain. It has demonstrated adequate internal reliability and face validity.³⁴ These items will be administered at baseline, 12 months, and 24 months. Given that young adults may demonstrate different levels of financial independence, those who indicate that they are not primarily responsible for paying for their medical care will respond to only two items regarding financial stress at baseline only. Those who indicate financial responsibility at baseline and everybody at 12 months, and 24 months follow-up, will respond to the full 11-item scale.
- Oncology Screening Tool, which is an adapted version of the NCCN Distress Thermometer and problem checklist to include problems specific to young adults. Participants first rate their distress on a 0-10 scale. Next, they are asked to check off areas of concern from the past week, including practical (e.g., housing arrangements, work, bills, transportation), family (e.g., parents, siblings, partner), emotional (e.g., sadness, isolation, guilt), social (e.g., isolation from friends, missing important events), physical (e.g., body image, sexual concerns, sleeping difficulty), and informational (e.g., understanding information, feeling involved in decision-making) needs. A total score from 0 to 51 is calculated. This checklist is used to prompt selection of problems to be addressed in the intervention for those assigned to receive the intervention.
- Demographic/Medical: Patients will report age, sex, independent living status, race, ethnicity, school/work status, health insurance coverage, marital status, whether he/she is a parent, and income. Potentially time-varying characteristics (i.e., school/work status, insurance status, income) will be repeatedly assessed at all follow-up surveys. Cancer diagnosis, date of diagnosis, and treatment received (e.g., chemotherapy, radiation, hematopoietic stem cell transplant), will be abstracted from the medical record by research staff. This information will be used to describe the sample and used as

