- covariates in the model (except for sex, which will be evaluated as a moderator). Observational research with adolescents and young adults found being on treatment and not being in school or working to be the primary drivers of distress rather than age, race, or cancer type.³⁶
- Supportive Services Received will be measured via self-report where participants will check whether they have used or received services in the following categories: psychosocial support, informational and practical support, fertility or sexual health, physical/wellness services and integrative medicine services) since diagnosis (at baseline) or the prior survey (at 3, 6, 12, and 24 months). If they check yes, they will be asked to specify the service used.
- PROMIS Social Isolation –Short Form 4a is a four-item measure assessing perceptions of social isolation from the NIH Patient-Reported Outcomes Measurement Information System (PROMIS.) ^{29,30} Each question uses a 5-point rating scale from 1 (*never*) to 5 (*always*) in the past 7 days, with higher scores indicating higher levels of perceived isolation.
- O Participant Satisfaction will be assessed using a 10-item questionnaire derived from the Multi-Dimensional Treatment Satisfaction Meausre³⁷ to assess utility of intervention-specific components (e.g., the user manual, worksheets), attitude towards the intervention, trainer competence, and perceived benefit attributable to the intervention, plus 3open-ended questions eliciting ideas for improvements. This questionnaire will only be administered at post-intervention to intervention arm only (3 months).
- Coronavirus Impact Scale³⁸ is a 12-item scale to assess how COVID-19 has changed a person's life (e.g., routine, family income, food access, medical and mental health access, access to family and friends, etc.) This will be administered at baseline.

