■ Subject Identifiers: We will collect participant name, address, telephone number, and email address for contact purposes throughout the study. Each participant will be assigned a participant ID number and we will keep a key linking the ID number to name for up to 6 years after the close of the study. We will collect MRN, date of birth, and date of diagnosis to abstract medical treatment data, calculate age, and calculate time since diagnosis. At the conclusion of the study, identifiers will be removed from the database and de-identified data kept indefinitely.

B. Secondary Data Collection

- Type of Records: Medical records will be accessed to abstract: date of birth, date of diagnosis, type of diagnosis to determine eligibility and describe the study sample. At the last survey follow-up, records will be accessed to document treatment(s) received, relapse status, comorbid psychological conditions, any documented social concerns, hospice referral, COVID-19 vaccination history, and use of psychosocial services. For those subjects who do not remain in the study until last follow-up due to various reasons (e.g., no longer interested, deceased, etc), data abstraction will occur at time subjects are exited from the study or as soon as practical.
- Location: Research staff with authorization to access medical records will access the medical records at each site using an authorized workstation to access the record.
- Inclusion/Exclusion: See Inclusion/Exclusion criteria in section 4.1C.
- Data Abstraction Form(s): See Data Abstraction Form.

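### The Aim 1 model leaves room for covariates measured after randomisation in the primary 6-month contrast, and section 6.1 names only one of the two randomisation strata

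*Combined protocol and SAP*

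**What the plan says.** **Section 6.1, Aim 1.** Efficacy is assessed with one repeated-measures linear model, fitted by maximum likelihood to all randomised participants. The primary endpoint is the change from baseline to 6 months, taken from the time and time-by-arm terms. Site is a fixed effect. A list of the method's benefits includes that "time varying covariates (such as school/employment status, treatment status (on treatment vs. completed), utilization of usual psychosocial care) can be incorporated into the model". Four sensitivity analyses follow: with and without site, per protocol, "adjustment for imbalance in baseline characteristics, if applicable", and racial/ethnic differences.

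**Section 1.9, Demographic/Medical.** "Potentially time-varying characteristics (i.e., school/work status, insurance status, income) will be repeatedly assessed at all follow-up surveys". On their use, the text reads "This information will be used to describe the sample and used as" and continues "covariates in the model (except for sex, which will be evaluated as a moderator". It does not say which model is meant, or whether baseline or follow-up values are to be used.

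**Section 1.9, Supportive Services Received.** Participants report services used "since diagnosis (at baseline) or the prior survey (at 3, 6, 12, and 24 months".

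**Section 1.9 B, Secondary Data Collection.** "At the last survey follow-up, records will be accessed to document treatment(s) received, relapse status". For those who leave early, abstraction happens at exit or as soon as practical.

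**Section 1.3 A, Research Procedures.** "The study biostatistician will determine a randomization scheme stratified by site, age group". Completing the baseline survey triggers assignment.

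**The concern.** Aim 1 asks what assignment to the intervention does, by intent to treat. How the effect arises is left to Aim 2. A covariate measured after assignment may itself have been changed by assignment. Adjusting for it then removes from the arm contrast whatever part of the effect passes through it. If the covariate and the outcome share unmeasured causes, adjusting can also add bias of its own.

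The variables named in section 6.1 are candidates for this. In the pilot (section 1.4), patients used the intervention on problems such as returning to school or work. Use of psychosocial services could be raised by referrals made in sessions, or lowered if participants cope better. An analyst who acted on the sentences in sections 6.1 and 1.9 could put such values into the primary model without departing from the plan. The choice could also be made after the data are seen.

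A smaller, separate matter is that randomisation is stratified by two factors and section 6.1 carries only one of them into the model.

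**Working it through.** The plan gives no figure on this point, so there is none to reproduce. The check is mainly a reading of the text, followed by an illustration of scale.

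**1. When the variables are measured**

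| Variable | Follow-up measurement | Basis for use as a covariate |
|---|---|---|
| School/work status | every follow-up survey (1.9) | permitted in 6.1; stated for an unnamed model in 1.9 |
| Insurance, income | every follow-up survey (1.9) | stated for an unnamed model in 1.9 |
| Use of psychosocial services | period since the prior survey (1.9) | permitted in 6.1 only |
| On treatment or completed | source not stated in 6.1 | permitted in 6.1 |
| Treatment received | charts read at last follow-up or exit (1.9 B) | stated for an unnamed model in 1.9 |

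Assignment follows the baseline survey, so the 6-month service-use item covers roughly months 3 to 6 and is post-randomisation by construction. The same holds for school/work status recorded at 3 or 6 months.

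**2. What is committed, permitted and unsaid.** Committed: time, time-by-arm, site. Permitted: time-varying covariates. Stated without model or timing: the demographic/medical set. Unsaid: any final covariate list, or any limit to baseline values for the primary contrast.

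**3. Do the documents show that the arms differ?** No.
- *School/work:* the pilot reports problems worked on, not changes in status. The trial population is also narrower than the pilot's (section 1.5: no recurrence, within 4 months of first diagnosis).
- *Service use:* referral during sessions exists only in the intervention arm (section 4.7 D). Survey-triggered referral, staff referral and the resource list cover both arms (sections 1.6, 4.7, 6.3), so the direction is open.
- *Treatment status:* nothing suggests an arm effect.

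**4. Illustration for school/work status.** Only 0.26 (depression, section 1.5) comes from the documents; the other inputs are assumed.

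Adjusted effect = 0.26 − (arm difference in the covariate × covariate effect on outcome)

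| Arm difference | Effect 0.2 SD | Effect 0.4 SD |
|---|---|---|
| 0 points | 0.26 | 0.26 |
| 5 points | 0.26 − 0.01 = 0.25 | 0.26 − 0.02 = 0.24 |
| 10 points | 0.26 − 0.02 = 0.24 | 0.26 − 0.04 = 0.22 |

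The losses are 0.01/0.26 = 3.8%, 0.02/0.26 = 7.7% and 0.04/0.26 = 15.4%. A 10% loss (0.026) needs 0.026/0.4 = 6.5 points or 0.026/0.2 = 13 points.

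A simulation in the form of the planned model agrees (344 randomised 1:1; baseline, 3 and 6 months as responses; unstructured covariance; 30% missing by 6 months; within-person correlation 0.6; 600 replicates). Adjusting reduced the 6-month contrast by −0.001 (0 points × 0.4), 0.010 (5 × 0.2), 0.019 (5 × 0.4), 0.019 (10 × 0.2) and 0.038 (10 × 0.4), with Monte Carlo error about 0.001.

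**5. Two limits on these numbers**
- *They are small against sampling error.* With 172 × 0.7 = 120.4 completers per arm and correlation 0.6, the standard error of the change contrast is about √(4 × 0.4/120.4) = 0.115. Shifts of 0.01 to 0.04 are 0.09 to 0.35 standard errors.
- *They are not a bound.* In a simplified single-visit model, suppose the arm moves the covariate by 0.2 SD and its effect is 0.3. The adjusted effect is 0.26 − 0.2 × 0.3 = 0.20. Add an unmeasured cause with weight 0.4 on both covariate and outcome, and it is 0.26 − 0.2 × (0.3 + 0.4 × 0.4) = 0.168.

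**6. Precision given up by not adjusting.** For a school/work-type covariate, the simulated ratio of adjusted to unadjusted standard error was 0.966 to 0.994. For treatment status, assume all are on treatment at baseline and half at 6 months. The reduction in standard error is 1 − √(v/(v + 0.25b²)), where v = 2(1 − correlation) and b is the covariate effect in SD:
- correlation 0.5, b = 0.2: 0.5%
- correlation 0.6, b = 0.4: 2.4%
- correlation 0.7, b = 0.6: 6.7%

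**7. Age group.** The usual rule is that the analysis should reflect the factors used to stratify. Section 6.1 names site but not age group; section 1.9 lists age among the variables for its unnamed model. The gain may be slight. Section 1.9 cites research in which age was not a main driver of distress. A time-constant main effect also drops out of a within-person change when data are complete, so it acts mainly through incomplete records unless it is crossed with time.

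**The case against.** The strongest reply is that section 6.1 does not specify follow-up covariates at all. The clause sits in a list of generic advantages and says only what the method allows. The committed wording describes a lean model, and adjusting for baseline imbalance as a sensitivity analysis makes little sense if the primary model is already heavily adjusted. This stands. A reader might infer that the plan commits the primary contrast to post-randomisation covariates, and the text does not support that. It also answers the complaint that no listed sensitivity analysis refits without them: if they are not in the primary model, no refit is needed, and the list is not stated to be exhaustive.

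Other stronger readings also fail:
- *Service use* rests on the permissive clause alone. The covariate sentence in section 1.9 belongs to the Demographic/Medical item, and the Supportive Services item has no such statement.
- *Late chart abstraction* does not by itself make treatment received a post-baseline value. Eligibility (section 4.1 C) already requires chemotherapy, radiation or transplant, so part of this is settled at entry. Only what is decided later is post-randomisation.
- *A bias of up to 15%* is one corner of an assumed grid. It is neither a finding nor a ceiling.

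The authors also give a reason for interest in these variables: section 1.9 cites being on treatment and being out of school or work as drivers of distress. That supports their prognostic value, but it equally supports the covariate effect on which any distortion depends.

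What remains is that section 1.9 says these data will be covariates, gives no model or timing, and nothing elsewhere excludes follow-up values from the primary contrast.

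**Conclusion.** The point holds as a gap in the specification that should be closed before analysis. The plan permits post-randomisation school/work status, treatment status and service use in the model that yields the primary 6-month contrast. For school/work status and other re-measured demographics, section 1.9 can be read as calling for it. If such values enter and the arms differ on them, the contrast no longer estimates the total intent-to-treat effect. If they do not enter, or the arms do not differ, there is no distortion.

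The size is unknown. The range from 0.26 down to 0.22 rests on assumed arm differences, assumed covariate effects and no shared unmeasured cause. For service use not even the direction can be given. The omission of age group from section 6.1 is a minor addition that can be corrected in the same edit. Confidence is medium: the wording is clear, but the consequence depends on choices and arm differences that the documents do not settle.

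**What to change.** - **Section 6.1, primary model.** State that it contains arm, time, arm-by-time, site, the age-group stratum and, if wanted, a pre-specified list of covariates measured at or before baseline. Keep the baseline outcome as a response, as the change contrast requires. Say whether site and age group enter as main effects only or also crossed with time.
- **Section 6.1, supplementary analysis.** Move adjustment for follow-up school/work status, on/completed treatment status and service use to a labelled supplementary analysis that does not drive the efficacy conclusion.
- **Section 1.9, Demographic/Medical.** Name the model and limit it to baseline values. Allow treatment information in the primary model only where it was fixed at entry.
- **Reporting.** Tabulate follow-up school/work status and service use by arm, so readers can see whether the arms diverged.

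This costs a few sentences and no new data. The downside is a small loss of precision from leaving out follow-up prognostic covariates, on the scale worked out above.
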